6.2.1. Preparation and Dispensing

Within this protocol, preparation refers to the investigator site activities performed to make the study intervention ready for administration or dispensing to the participant by qualified staff. Dispensing is defined as the provision of study intervention, concomitant treatments, and accompanying information by qualified staff member(s) to a healthcare provider, participant, in accordance with this protocol. Local health authority regulations or investigator site guidelines may use alternative terms for these activities.

Sisunatovir and placebo will be prepared by qualified unblinded site personnel according to the IPM. Blinded study intervention will be administered in a blinded fashion to the participant. See the IPM for instructions on how to prepare the study intervention for administration or palatability assessment. Capsules will be prepared at the CRU in the individual dosing containers by 2 operators, 1 of whom is an appropriately qualified and experienced member of the study staff (eg, physician, nurse, physician's assistant, nurse practitioner, pharmacy assistant/technician, or pharmacist).

6.3. Assignment to Study Intervention

The investigator will assign participant numbers to the participants as they are screened for the study. Pfizer will provide a randomization schedule to the investigator and, in accordance with the randomization numbers, the participant will receive the study treatment regimen assigned to the corresponding randomization number.

6.4. Blinding

The first 2 periods of each cohort are double blind (sponsor open) design.

Study intervention administrated in Periods 3 to 7 of the study will be open to the participant, Investigator and Sponsor or Sponsor-designate personnel responsible for study monitoring activities (including all site monitoring activities).

6.4.1. Blinding of Participants

Participants will be blinded to their assigned study intervention. Study intervention administrated in Periods 3 to 7 of the study will be open to participant.

6.4.2. Blinding of Site Personnel

Investigators and other site staff will be blinded to participants' assigned study intervention. Study intervention administrated in Periods 3 to 7 of the study will be open to Investigator and other site staff.

Participants will be assigned to receive study intervention according to the assigned treatment group from the randomization scheme.

In the first 2 periods, in order to maintain the blind, an otherwise uninvolved third party will be responsible for the preparation and dispensing of all study intervention and will endeavor to ensure that there are no differences in time taken to dispense or visual presentation, following randomization or dispensing.

In the event of a Quality Assurance audit, the auditor(s) will be allowed access to unblinded study intervention records at the site(s) to verify that randomization/dispensing has been done accurately.

6.4.3. Blinding of the Sponsor

As this is a sponsor open study, a limited number of the sponsor's team members (excluding site staff) may conduct unblinded reviews of the data during the course of the study for the purpose of safety and tolerability assessment, facilitating PK/PD modeling, and/or supporting clinical development.

6.4.4. Breaking the Blind

Blood specimens will be obtained from all participants for PK analysis to maintain the study blind at the investigator site. Only the investigator site staff and blinded study monitor, if assigned, will be blinded to study treatment for Periods 1 and 2. Other Pfizer personnel will be unblinded to participant treatments in order to permit real-time interpretation of the safety and PK data; and provide information necessary to further clinical development. The blinded study monitor, if assigned, will remain blinded to treatment until all monitoring for the study has been completed. Specimens from participants randomized to placebo will not be routinely analyzed. To minimize the potential for bias, treatment randomization information for Periods 1 and 2 will be kept confidential by Pfizer unblinded personnel and will not be released to the blinded investigator or blinded investigator site personnel until the study database has been locked or the investigator requests unblinding for safety reasons.

6.5. Study Intervention Compliance

When the individual dose for a participant is prepared from a bulk supply, the preparation of the dose will be confirmed by a second qualified member of the study site staff.

When participants are dosed, they will receive study intervention directly from the investigator or designee, under medical supervision. The date and time of each dose administered in the clinic will be recorded in the source documents and recorded in the CRF. The dose of study intervention and study participant identification will be confirmed at the time of dosing by a member of the study site staff. Study site personnel will examine each participant's mouth to ensure that the study intervention was ingested.

6.6. Dose Modification

Dose in Periods 2 and 3 of Cohort 1 may be reduced based on safety and PK observations in previous periods (see [Section 4.1](#)). The dose for Cohort 2 (if conducted) will be chosen based on data from Cohort 1 and will not exceed 400 mg Q12 hours.

6.7. Continued Access to Study Intervention After the End of the Study

No study intervention will be provided to participants at the end of their study participation.

6.8. Treatment of Overdose

For this study, any dose of sisunatovir greater than 1200 mg within a 24-hour time period will be considered an overdose.

There is no specific treatment for an overdose.

In the event of an overdose, the investigator should:

1. Contact the study medical monitor within 24 hours.
2. Closely monitor the participant for any AEs/SAEs and laboratory abnormalities as medically appropriate and at least until the next scheduled follow-up.
3. Document the quantity of the excess dose as well as the duration of the overdose in the CRF.
4. Overdose is reportable to Pfizer Safety **only when associated with an SAE**.
5. Obtain a blood sample for PK analysis if requested by the study medical monitor (determined on a case-by-case basis).

Decisions regarding dose interruptions or modifications will be made by the investigator in consultation with the study medical monitor as needed based on the clinical evaluation of the participant.

6.9. Prior and Concomitant Therapy

Use of prescription or nonprescription drugs and dietary and herbal supplements are prohibited within 7 days or 5 half-lives (whichever is longer) prior to the first dose of study intervention. Limited use of nonprescription medications that are not believed to affect participant safety or the overall results of the study may be permitted on a case-by-case basis

following approval by the sponsor. Acetaminophen/paracetamol may be used at doses of ≤ 1 g/day.

Females using hormonal contraceptives or taking hormone replacement therapy may be eligible to participate in this study if they are willing to discontinue therapy at least 28 days prior to the first dose of study treatment and remain off hormonal therapy for the duration of the study. DepoProvera® must be discontinued at least 6 months prior to the first dose of study treatment.

All concomitant treatments taken during the study must be recorded with indication, daily dose, and start and stop dates of administration. All participants will be questioned about concomitant treatment at each clinic visit.

Treatments taken within 28 days before the first dose of study intervention will be documented as a prior treatment. Treatments taken after the first dose of study intervention will be documented as concomitant treatments.

7. DISCONTINUATION OF STUDY INTERVENTION AND PARTICIPANT DISCONTINUATION/WITHDRAWAL

7.1. Discontinuation of Study Intervention

It may be necessary for a participant to permanently discontinue study intervention. Reasons for permanent discontinuation of study intervention include the following:

- AE requiring discontinuation in investigator's view.
- Pregnancy.

If study intervention is permanently discontinued, the participant will not remain in the study for further evaluation. See the [SoA](#) for data to be collected at the time of discontinuation of study intervention. In the event of discontinuation of study intervention, it must be documented on the appropriate CRF/in the medical records whether the participant is discontinuing further receipt of study intervention or also from study procedures, posttreatment study follow-up, and/or future collection of additional information.

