2.2.3. Nonclinical Safety

- In the repeat dose toxicity studies in adult (up to 28 days) and neonatal/juvenile rats and dogs, the MTDs were defined by body weight loss and reduced food consumption accompanied by adverse clinical observation of varying severity. In dogs, there was dose-related incidence of emesis and liquid feces at ≥ 15 mg/kg/day. The key target organ for toxicity in adult animals was the hepatobiliary system, which included both degenerative and inflammatory changes in bile duct, in rats (≥ 60 mg/kg/day) and dogs (≥ 45 mg/kg/day). In dogs, the hepatobiliary findings correlated with elevated plasma levels of ALP, ALT and GGT. In addition, the findings observed only in rats were in kidney (degeneration/regeneration of medullary tubules) at ≥ 120 mg/kg/day, lung (vascular degeneration/necrosis) at 240 mg/kg/day (non-tolerated dose) and trachea (epithelial degeneration and subepithelial inflammation [predominantly in females]) at 120 mg/kg/day in 14 and/or 28-day studies. In the 28-day dog repeat dose toxicity study, the NOAEL was 15 mg/kg/day corresponding to C_{max} of 729 ng/mL and AUC_{tau} of 9510 ng.h/mL. In the 28-day rat repeat dose toxicity study, the NOAEL was 60 mg/kg/day corresponding to C_{max} of 322 ng/mL and AUC_{tau} of 4725 ng.h/mL.
- In the embryo-fetal toxicity studies in rat (GD6-17) and rabbit (GD6-18), there were no effects on pregnancy or embryo-fetal development. In rat, the NOAEL for maternal toxicity was 45 mg/kg/day based on the transient initial body weight loss followed by dose-related decreased body weight gain at ≥ 45 mg/kg/day. The NOAEL for embryo-fetal toxicity in rat was 60 mg/kg/day, corresponding to systemic maternal exposure (AUC_{24}) of 9830 ng.h/mL on Day 15 of gestation. In rabbit, maternal toxicity was limited to lower body weight gain and food intake at 45 mg/kg/day. The NOAEL for embryo-fetal development in rabbit was 45 mg/kg/day, corresponding to a systemic maternal exposure (AUC_{24}) of 220 ng.h/mL on Day 16 of gestation.

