TEAEs were in the GI disorders SOC; nausea, diarrhea and abdominal pain. These TEAEs have been mild to moderate in intensity and resolved without sequelae. Most events attributed to IMP involved the gastrointestinal tract with nausea, diarrhea, and abdominal pain/discomfort/distension being the most common and occurring more commonly with the 350 mg dose of sisunatovir than with the 200 mg sisunatovir dose, where the number of participants reporting these events were lower and similar to those on placebo. In children, sisunatovir is required to be suspended in a solution to enable oral administration, there has been evidence of poor tolerability when sisunatovir was suspended in water as a single dose of 2.0 mg/kg in children aged 6-36 months, resulting in expulsion of the oral dose. Suspension in breast milk, formula milk or saline appeared to improve the palatability, with all doses being successfully administered to children aged 1 to 36 months in study C5241003.

As of 28 October 2022, there have been no SAEs attributable to sisunatovir and no deaths in the clinical studies.

In adults, sisunatovir is slowly absorbed reaching maximum plasma concentrations (t_{max}) at 5-6 hours (hrs) with a relatively moderate clearance, resulting in a half-life of 7-10 hours in healthy participants. Dosing to steady state resulted in steady state concentrations being reached after approximately 2 days of dosing resulting in 2-4 fold accumulation of exposure. AUC and C_{max} values increased in a greater than dose proportional manner across single and multiple dose studies. Following 5 days of dosing, the variability in PK parameters was high, with % CV ranging from 67.4-84% for C_{max} and 71.9-144% for AUC₁₂.

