The effect of food on the single dose pharmacokinetics was assessed for the DIC and DPB dispersed in water. For the DIC the extent of systemic exposure to sisunatovir (geometric mean AUC_{inf} under fed and fasted conditions) was 357 and 221 ng.h/mL respectively, with the between-subject variability being lower under fed conditions (CV 64.1% compared with 198%). The ratio of fed/fasted was 218% (90% CI 94.2 - 502%) for C_{max} and 162% (90% CI 83.0 – 316%) for AUC_{0-inf}. For the DPB dispersed in water the extent of systemic exposure to sisunatovir (geometric mean AUC_{0-∞}) under fed and fasted conditions was 371 and 337 ng.h/mL respectively, with the between-subject variability being slightly lower under fasted conditions (CV 49.0% compared with 61.6%). The ratio of fed/fasted was 107.7% (90% CI 78.0 – 148.8%) for C_{max} and 110.0% (90% CI 85.6 – 141.4%) for AUC_{0-inf}. Inter-individual variability as illustrated by the %CV geometric mean suggests this was greater following administration of DPB in the fed state.

Clinical DDI Study C5241004 demonstrated that the disposition of sisunatovir is expected to be affected by moderate to strong inhibitors and inducers of CYP3A4. Furthermore, sisunatovir was demonstrated to be a moderate inhibitor of CYP3A4, so dose adjustments for compounds that are sensitive substrates for CYP3A4 may need to be considered.

In an RSV challenge study, sisunatovir treatment resulted in a statistically significant reduction in AUC of RSV viral load compared with placebo; 55.25% (p=0.007) and 63.05% (p=0.002) for the 200 mg and 350 mg sisunatovir dose groups respectively (dosed Q12 hours for 5 days). Results for the AUC of total symptom score were consistent with the

viral load AUC. Geometric mean AUCs of total symptom score were 195.56, 30.79 and 31.76 hours x score for placebo, 200 mg sisunatovir and 350 mg sisunatovir, respectively. The reduction in AUCs of total symptom score compared with placebo was statistically significant for both sisunatovir treatment groups; $p=0.009$ (70.84%) and $p=0.002$ (74.42%), (Wilcoxon Rank-Sum test) for the 200 mg and 350 mg sisunatovir dose groups, respectively.

More detailed information about results of clinical studies for sisunatovir may be found in the IB, which is the SRSD for this study.

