2.3.1. Risk Assessment

Potential Risk of Clinical Significance	Summary of Data/Rationale for Risk	Mitigation Strategy
Study Intervention: sisunatovir		
Hepatobiliary system effects	Degenerative and inflammatory changes in the bile duct of both rats (≥ 60 mg/kg/day) and dogs (≥ 45 mg/kg/day) in studies of up to 28 days, with elevated plasma levels of ALP, ALT and GGT in dogs only. Evidence of recovery for all findings following a 14-day treatment-free period.	Standard monitoring including laboratory (ie, transaminases, ALP, GGT) and AE monitoring.
Gastrointestinal effects	Transient dose-related incidence of emesis and liquid feces in dogs at doses ≥ 15 mg/kg/day in studies up to 28 days. Additionally, inflammation in duodenum, gall bladder, and liver at 45 mg/kg/day noted in 28-day dog study. In previous clinical studies sisunatovir has been associated with mild GI AEs.	As this is an investigational agent, there is some risk that is mitigated by close observation of AEs, etc. Participants will be closely evaluated in an inpatient setting to monitor for GI AEs. If needed, palliative alleviating measures such care as antiemetics may be provided.

Potential Risk of Clinical Significance	Summary of Data/Rationale for Risk	Mitigation Strategy
Renal effects	Degeneration/regeneration of medullary tubules was noted in rats at ≥ 120 mg/kg/day in studies of up to 28 days; considered non-adverse based on lack of clinical pathology changes.	Standard monitoring including laboratory and AE monitoring.
Cardiovascular effects	Myocardial degeneration and necrosis was noted at 240 mg/kg/day (non-tolerated dose) in a 14-day rat study. No similar effect in rats at 120 mg/kg/day in the 28-day study, or in dogs at any dose, for 14 or 28 days.	Monitoring will include vital signs, including heart rate, and ECG assessments.
Pulmonary effects	Vascular degeneration/necrosis in lung at 240 mg/kg/day and epithelial degeneration/necrosis in trachea at 120 mg/kg/day in 14-day rat study. No similar effect in rats at 120 mg/kg/day in the 28-day study, or in dogs at any dose, for 14 or 28 days. Phase 1 FIH study (C5241001) showed no adverse clinically significant changes in safety laboratory parameters (including troponin), ECGs and vital signs.	There will be standard safety monitoring including vital signs and of adverse events.

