4. STUDY DESIGN

4.1. Overall Design

This is a Phase 1 study that will be conducted in up to two cohorts.

Cohort 1 is a randomized, 2-part, crossover design. Part 1 has 3 periods, Periods 1 and 2 are double blind, sponsor open, placebo controlled crossover design to evaluate the safety and tolerability and PK of the planned 400 mg and 200 mg of sisunatovir given Q12 hours x 4 days plus 1 dose as 50 mg capsules in a fed state. Period 3, is an open label period to evaluate the food effect of the planned 400 mg of sisunatovir given Q12 hours x 4 days plus 1 dose in a fasted state. Part 2, Periods 4-7, is open label to assess the palatability of 50 mg of sisunatovir in 4 different vehicles (water, infant formula, apple juice, and saline) in a randomized crossover design.

Cohort 1 will include approximately 12 participants that will be randomized into 4 sequences with 3 participants in each sequence. Each sequence will receive treatment in a pre-specified manner ([Section 1.2 Schema](#)).

Participants will be admitted to the CRU on Day -1 to undergo baseline procedures. Over the first 2 periods, all participants are planned to receive (A) 400 mg and either (B) 200 mg plus matching placebo or (C) placebo dosed Q12 hours for 4 days plus 1 dose in the fed state. All participants in Period 3 will receive (D) 400 mg dosed Q12 hours for 4 days plus 1 dose in the fasted state. Note that the dose levels for Periods 2 and 3 are dependent upon the PK in the previous periods as described below.

Prior to proceeding to Period 2 of Cohort 1, the Period 1 Day 5 PK up to 12 hours post-dose will be assessed. If the mean exposures (AUC or Cmax) at 400 mg in Period 1 exceeds the rat (most sensitive species) NOAEL, the doses for the subsequent period(s) will be capped to a dose that is not expected to exceed the rat NOAEL. Similarly, prior to proceeding to Period 3 of Cohort 1, the Periods 1 and 2 Day 5 PK up to 12 hours post-dose will be assessed, and if the mean exposures (AUC or Cmax) at 400 mg exceeds the rat (most sensitive species) NOAEL, the doses for the subsequent period(s) will be capped to a dose that is not expected to exceed the rat NOAEL. Furthermore, safety will also be assessed following each period and doses for subsequent periods may be reduced if the safety and tolerability of the previous dose was not deemed sufficiently tolerated.

A minimum 7-day washout period will occur between the last dose of Periods 1 and 2 and the first dose of Periods 2 and 3.

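### Section 7.1 sets numeric stopping limits for QTcF and creatinine but none for liver tests, although the hepatobiliary system is the key target organ in animals

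*Protocol*

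**What the plan says.** **Stopping rules.** Under "Reasons for permanent discontinuation of study intervention include the following", Protocol Section 7.1 gives two reasons: an adverse event needing discontinuation in the investigator's view, and pregnancy. Section 7.1.1 makes withdrawal mandatory at QTcF above 500 ms or a change from baseline above 60 ms. Section 7.1.2 calls for a repeat when creatinine rises by 0.3 mg/dL or more, and for discontinuation if the second value is 0.4 mg/dL or more. It also calls for an adverse-drug-reaction assessment if two or more participants in a period have two consecutive results of 0.3 mg/dL or more. Sections 7.1 to 7.3 and 8.3.4 contain no limit for AST, ALT, ALP, GGT or bilirubin.

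**The liver signal.** Section 2.2.3 states: "The key target organ for toxicity in adult animals was the hepatobiliary system". Bile-duct changes were seen in rats and dogs, with raised ALP, ALT and GGT in dogs. The mitigation in the Section 2.3.1 risk table is "Standard monitoring including laboratory (ie, transaminases, ALP, GGT) and AE monitoring".

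**Appendix 6.** Transaminases above 3 x ULN call for more frequent monitoring. With normal baseline values, a potential Hy's law case needs AST or ALT at least 3 x ULN, bilirubin at least 2 x ULN, no hemolysis, and ALP below 2 x ULN or unavailable. It leads to evaluation and, once confirmed on repeat, to SAE reporting. The appendix also says that liver tests are not routine here, whereas Table 6 (Appendix 2) lists all five as required.

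**Other safeguards.** Section 4.1 provides a review after each period: "doses for subsequent periods may be reduced if the safety and tolerability of the previous dose was not deemed sufficiently tolerated". SAP Section 3.5.2 takes the laboratory baseline on Day -1 of each period, and Protocol Section 9.3.2 has safety data reviewed on an ongoing basis.

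**The concern.** The organ that the animal data put first is the one without a stopping number. Kidney findings appeared only in rats, at 120 mg/kg/day or more, and were considered non-adverse. Myocardial findings appeared only at a non-tolerated 240 mg/kg/day. Both organs are covered by numeric limits. Those limits are sound; the point is that the liver deserves the same treatment.

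The written rules would allow a healthy volunteer to start a new 9-dose course after a confirmed transaminase above 3 x ULN, provided that monitoring is closer and the investigator sees no reason to stop. Participants have no expected benefit, 400 mg every 12 hours is the highest multiple dose yet given, and all of Cohort 1 are planned to receive it in two courses. A limit fixed in advance makes the decision predictable and keeps it from being set after the values are seen.

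**Working it through.** The plan states no figure on this point, so the main check sets liver patterns against the written rules.

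**Step 1. What each pattern triggers (normal baseline assumed)**

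| Pattern | Written response | Numeric stop? |
|---|---|---|
| QTcF >500 ms, or change >60 ms | Withdrawal (7.1.1) | Yes |
| Creatinine +0.3, then at least 0.4 mg/dL on repeat | Discontinuation (7.1.2) | Yes |
| ALT 10 x ULN, bilirubin <2 x ULN | More frequent monitoring (Appendix 6) | No |
| ALP >=2 x ULN, ALT <3 x ULN | Repeat if judged clinically significant (8.3.4) | No |
| ALT >3, bilirubin >=2, ALP >=2 x ULN | More frequent monitoring; outside the Hy's law definition | No |
| Full potential Hy's law case | Evaluation and SAE reporting | No |

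In the four liver rows, stopping depends on the investigator's view under 7.1.

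**Step 2. Does the exposure cap limit individuals?** The Section 4.1 cap acts on mean exposure. Section 4.3 projects a 1.2-fold margin to the rat NOAEL, and Section 2.2.4 says: "Following 5 days of dosing, the variability in PK parameters was high".

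Inputs:
- Day 5 CVs from earlier studies: 67.4-84% for Cmax and 71.9-144% for AUC.
- Single-dose CVs of 49.0% and 61.6%, which are for powder blend dispersed in water, not for the capsules used here.
- NOAEL AUC and Cmax (Section 2.2.3): rat 4725 ng.h/mL and 322 ng/mL; dog 9510 ng.h/mL and 729 ng/mL.

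Assumptions: exposure is lognormal, and its arithmetic mean is the rat NOAEL divided by 1.2.

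Formulas: sigma = sqrt(ln(1 + CV^2)); P(exceed) = 1 - Phi((ln m + sigma^2/2)/sigma), where m is the margin.

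Margins: rat 1.2; dog AUC 1.2 x 9510/4725 = 2.42; dog Cmax 1.2 x 729/322 = 2.72.

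| CV | sigma | Rat, m = 1.2 | Dog AUC, m = 2.42 | Dog Cmax, m = 2.72 |
|---|---|---|---|---|
| 49.0% | 0.464 | 26.6% | 1.6% | 0.9% |
| 61.6% | 0.567 | 27.3% | 3.3% | 2.0% |
| 67.4% | 0.612 | 27.3% | 4.0% | 2.6% |
| 71.9% | 0.646 | 27.3% | 4.6% | 3.1% |
| 84% | 0.731 | 26.9% | 5.8% | 4.2% |
| 144% | 1.060 | 24.1% | 8.7% | 7.0% |

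So 24-27% exceed the rat NOAEL (12 x 0.241 = 2.9 to 12 x 0.273 = 3.3 participants), and about 1-9% exceed the dog NOAEL (at most 12 x 0.087 = 1.0). The rat figure depends on the margin: 13-18% at 1.5 and 30-41% at 1.0. If 1.2 refers to geometric means, P = 1 - Phi(ln m/sigma), which gives 35-43% for rat, 3-20% for dog AUC and 2-17% for dog Cmax.

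**Step 3. Precision cost of withdrawals.** With the within-participant SD held fixed, the half-width of the paired 90% interval is proportional to t(0.95, n-1)/sqrt(n). For n = 12 this is 1.796/3.464 = 0.518; for n = 11, 1.812/3.317 = 0.546 (+5.4%); for n = 10, 1.833/3.162 = 0.580 (+11.8%).

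**The case against.** Several points on the other side stand.

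- **There are ways to stop.** A reader might infer that nothing protects participants. That is not so. The investigator can stop dosing for a liver adverse event, Appendix 6 has numeric triggers for monitoring and evaluation, Day -1 tests precede each course after a washout of at least 7 days, and safety is reviewed on an ongoing basis and between periods.
- **The exposure model does not count liver cases.** A reader might infer that about 3 of 12 participants would have liver effects. The documents do not support that. Section 2.3.1 says that liver enzymes rose in dogs only, and exceedance of the dog NOAEL is far rarer in the same model. The NOAEL comes from 28 days of dosing against 9 doses per course here. Section 2.3.1 also reports "Evidence of recovery for all findings following a 14-day treatment-free period" and says that the first-in-human study "showed no adverse clinically significant changes in safety laboratory parameters".
- **Liver tests will be drawn.** A reader might take the Appendix 6 sentence to mean that they will not. Section 8.3.4 makes the Appendix 2 tests mandatory, so the contradiction is editorial.
- **Specific limits are a choice.** The documents do not establish 2 x ULN for ALP or 3 x ULN for AST/ALT as withdrawal limits. The values are for the sponsor to confirm.

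None of this supplies a stopping number for the liver, or a case evaluation when ALP is at or above 2 x ULN.

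**Conclusion.** The gap is real, and closing it is a cheap improvement. Two organs have numeric stopping limits, the key target organ has none, and Appendix 6 leads to monitoring, evaluation and reporting but never to stopping. Its case definition also leaves out ALP at or above 2 x ULN, although ALP is one of the markers raised in dogs. This conclusion rests on the text alone and needs no model.

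The 24-27% figure shows only that a cap on the mean does not limit individual exposure. It depends on the lognormal form, CVs from earlier studies and the projected 1.2-fold margin. It is not an estimate of liver-test elevation or of harm.

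**What to change.** Add a liver subsection to Protocol Section 7.1, modelled on 7.1.2:

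- Stop study intervention for any potential Hy's law case, and for AST or ALT >=3 x ULN or ALP >=2 x ULN confirmed on a prompt repeat. The repeat should preferably be within 48 hours, as for creatinine, and always before dosing in a new period.
- Read GGT alongside ALP. The sponsor confirms the exact values. As a reference point, entry requires ALP not above ULN and AST/ALT below 1.5 x ULN, so each proposed limit is at least twice the highest value allowed at entry (2/1 and 3/1.5). That is arithmetic, not clinical justification.
- State that these participants are followed until values resolve, because Section 7.1 says that a permanently discontinued participant does not remain for further evaluation.
- If two or more participants in a period meet the rule, require an adverse-drug-reaction assessment.

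In Appendix 6, extend the evaluation to ALP >=2 x ULN, keep ALP <2 x ULN only for the Hy's law label, and delete the sentence that liver tests are not routine.

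**Cost.** No new scheduled samples, only confirmatory repeats. Replacement under Section 9.5 covers non-safety discontinuations only, so one or two withdrawals could leave 11 or 10 of 12 participants for the fed/fasted comparison. That would widen its 90% interval by about 5% or 12% on the log scale, which is acceptable where safety is the primary objective.
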